3.2 Rationale of study design

The secukinumab 300 mg s.c. every 4 weeks dose regimen has been evaluated extensively in a Phase 3 clinical trial program and showed strong sustainability of efficacy response with a good safety profile up to 52 weeks of treatment. Further knowledge for long term maintenance treatment flexibility for the optimal effective dose is a medical need that dermatologists are looking for with any biologic psoriasis drug in order to administer to the patient the right dose and regimen at the right treatment time.

The main reason for choosing the study design is to research in optimized maintenance treatment options to minimize drug exposure for secukinumab in patients cleared or almost cleared (PASI 90) from psoriasis while maintaining an acceptable clinical response and comparable safety profile.

Another reason for the study design is to examine if PASI 75 responders could benefit in terms of efficacy from an increased dosing interval for the study drug with a comparable safety profile. In the CAIN457A2212 study psoriasis patients have been exposed to an increased drug exposure without detection of any safety-related signals.

Taken together the rationale for the study is to explore options for individualizing maintenance treatment.

The CAIN457A2304 study, part of the secukinumab Phase 3 program, has assessed a RAN (retreatment at the start of relapse) approach as an alternative to maintain treatment response in some patients when secukinumab response has been achieved after 12 weeks. The fixed-dose interval regimen every 4 weeks was shown to have a clear benefit compared to the RAN regimen for sustained efficacy in the treatment of psoriasis (Mrowietz et al 2013).

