9.1 Analysis sets

The **Safety Set for Treatment Period 1 (SAF-TP1)** will include all patients who received at least one dose of study drug during this treatment period.

The Safety Set for Maintenance Treatment Period 2 (SAF-TP2) will include all patients who were randomized and received at least one dose of study drug at- or after the Week 24 visit. For safety evaluations, the patient groups of PASI 90 responders and PASI 75 responders who do not achieve a PASI 90 response will be pooled; therefore, only 3 dosing groups will be compared:

- secukinumab 300 mg s.c. every 2 weeks (patients from Group 4)
- secukinumab 300 mg s.c. every 4 weeks (patients from Group 1 pooled with Group 3)
- secukinumab 300 mg s.c. every 6 weeks (patients from Group 2)

Patients will be analyzed according to the treatment they received.

The Full Analysis Set for Treatment Period 2 of PASI 90 Responders (FAS-P90R) will include all patients who are rated as PASI 90 responders at the Week 24 visit, were randomized to treatment groups 1 or 2 and who received at least one dose of study drug at- or after visit Week 24.

The Full Analysis Set for Treatment Period 2 of PASI 75 Responders who do not achieve a PASI 90 Response (FAS-P75P) will include all patients who are rated as PASI 75 responders who do not achieve a PASI 90 response at visit Week 24, were randomized to treatment Group 3 or 4 and who received at least one dose of study drug at- or after visit Week 24.

The Per-Protocol Set for Treatment Period 2 of PASI 90 Responders (PP-P90R) will include all patients from the FAS-P90R who complete the study as scheduled without any major deviations from the protocol which may affect the primary outcome of this study. Such deviation will be defined in the Data Validation Plan or similar document and in the protocol of the blind data review without knowledge of the treatment group assignment.

Efficacy evaluations will be performed according to the treatment assigned at randomization.

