9.5.2 Safety variables

For safety-evaluations, the patient groups of PASI 90 responders and those who achieve PASI 75 but not PASI 90 will be pooled for Group 1 and Group 3; therefore, only 3 dosing groups will be compared:

- secukinumab 300 mg s.c. every 2 weeks (patients from Group 4).
- secukinumab 300 mg s.c. every 4 weeks (patients from Group 1 pooled with Group 3).

• secukinumab 300 mg s.c. every 6 weeks (patients from Group 2).

Patients will be analyzed according to the treatment they received.

Treatment emergent AEs (events started after the first dose of study drug or events present prior to the first dose of study drug but increased in severity based on preferred term) will be summarized. Only primary paths within MedDRA will be considered for AE reporting.

AEs will be summarized by presenting, for each treatment group, the number and percentage of patients

- having any AE,
- having an AE in each primary SOC and
- having each individual AE (preferred term).

Summaries will also be presented for AEs by severity and for study drug related AEs. If a patient reported more than one AE with the same preferred term, the AE with the greatest severity will be presented. If a patient reported more than one AE within the same primary SOC, the patient will be counted only once with the greatest severity at the SOC level, where applicable.

These summaries will be presented separately for study periods (Treatment Period 1, Treatment Period 2, Post-Treatment Follow-up Period), and for complete treatment periods (Treatment Periods 1 and 2 and Follow-up). Separate summaries will be provided for deaths, SAEs, other significant AEs leading to discontinuation and AEs leading to study drug discontinuation.

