### 1.2 Subjects and treatments

The following study periods will be considered for the analysis:

- Screening Period (Screening to Visit 2 [=Baseline], excluding Visit 2 [=Baseline])
- **Treatment Period 1** (Visit 2 [=Baseline] to Week 24 pre-dose)
- Treatment Period 2 (Week 24 post-dose to Week 52)
- Follow-Up Period (Week 52 to Week 60, excluding Week 52).

For Treatment Period 1 (Baseline to Week 24) all patients will receive the same treatment:

• Secukinumab 300 mg s.c. will be self-administered at Baseline, weekly at Week 1, Week 2 and Week 3 and every 4 weeks thereafter (i.e., Week 4, 8, 12, 16 and 20).

At Week 24, all patients will be assessed in term of PASI response and either randomized to one of the 4 treatment groups in Treatment Period 2 (Week 24 to Week 52) or withdrawn from the study. Randomization is stratified by body weight at this visit ("body weight  $\geq 90 \text{ kg}$ " vs. "body weight < 90 kg" at Week 24) in order to ensure balanced allocation of patients to treatment groups within the weight strata.

Patients with at least a 90% reduction in PASI score from Baseline will be randomized at Week 24 on a 1:1 basis to Group 1 or Group 2:

- **Group 1** (recommended maintenance treatment): secukinumab 300 mg s.c. every 4 weeks (Week 24, 28, 32, 36, 40, 44 and 48).
- **Group 2** (experimental dosing maintenance treatment): secukinumab 300 mg s.c. every 6 weeks (Week 24, 30, 36, 42 and 48).

Patients with less than 90% reduction in PASI score from Baseline at Week 24 but who achieved at least a 75% reduction in PASI score from Baseline are eligible for dose frequency intensification and will be randomized on a 1:1 basis to either Group 3 or Group 4:

- **Group 3** (recommended maintenance treatment): secukinumab s.c. 300 mg every 4 weeks (Week 24, 28, 32, 36, 40, 44 and 48).
- **Group 4** (experimental maintenance treatment): secukinumab s.c. 300 mg every 2 weeks (Week 24, 26, 28, 30, 32, 34, 36, 38, 40, 42, 44, 46 and 48).

Patients with a reduction in PASI score from Baseline of less than 75% at Week 24 are not eligible for randomization and are discontinued from the study.

The following analysis sets will be used for the data analysis.

Safety set for Treatment Period 1 (SAF-TP1): The safety set for Treatment Period 1 includes all subjects who took at least one dose of study treatment during this treatment period.

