#### 1.9 Standard safety evaluation

Safety analyses will be performed separately for Treatment Period 1, Treatment Period 2 and the Follow-Up period. Additionally, adverse events will be analyzed for the Entire Study Period combined (i.e. Treatment Period 1, Treatment Period 2).

Safety analyses for Treatment Period 1 will be based on the SAF-TP1, for Treatment Period 2 on the SAF-TP2, analyses for the post treatment Follow-Up period on the FUS and analyses for the Entire Treatment Period on the SAF-TP1.

#### Treatment groups for evaluation of Treatment Period 2

For safety-evaluations, the patient groups of PASI 90 responders and those who achieve PASI 75 but not PASI 90 will be pooled for Group 1 and Group 3; therefore, only 3 dosing groups will be analyzed in Treatment Period 2:

- Secukinumab 300 mg s.c. every 2 weeks (patients from Group 4).
- Secukinumab 300 mg s.c. every 4 weeks (patients from Group 1 pooled with Group 3).
- Secukinumab 300 mg s.c. every 6 weeks (patients from Group 2).

Additionally, the total number of patients over all groups will be analyzed in a separate column. Patients will be analyzed according to the treatment regimen they received.

If the treatment regimen of patients only deviates partially from the randomized treatment regimen during Treatment Period 2, these patients will be analyzed according to the treatment randomized.

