#### Treatment groups for evaluation of Follow-Up Period

For the analysis of the post treatment Follow-Up Period Group 3 and Group 4 defined in Section 1.2 will be used next to a combined group.

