#### Crude incidence and 100\*(1-α)% confidence interval 2.2.4

For n subjects, each at risk to experience a certain event with probability  $\pi$ , the crude incidence is estimated as p=x/n, where x is the number of subjects with the event.

Absolute and relative frequencies will be displayed as well as 95% confidence interval for the relative frequency based on the score method including continuity correction (Newcombe 1998).

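### Treatment Period 2 safety tables merge Group 1 with Group 3, and no adverse event or laboratory summary by the four randomised groups is planned beside them

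*SAP*

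**What the plan says.** SAP 1.2 describes two separate 1:1 randomisations at Week 24. PASI 90 responders go to Group 1 (4-weekly) or Group 2 (6-weekly). Patients with PASI 75 but not PASI 90 are "eligible for dose frequency intensification and will be randomized on a 1:1 basis to either Group 3 or Group 4" (4-weekly and 2-weekly respectively).

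SAP 1.9 then sets the Treatment Period 2 safety columns: PASI 90 responders and "those who achieve PASI 75 but not PASI 90 will be pooled for Group 1 and Group 3". The 2-weekly column is Group 4 alone, the 6-weekly column is Group 2 alone, and a total column is added. Protocol 9.5.2 has the same 4-weekly column: "secukinumab 300 mg s.c. every 4 weeks (patients from Group 1 pooled with Group 3". Protocol 9.1 adds, "therefore, only 3 dosing groups will be compared"; SAP 1.9 speaks of analysing them.

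Other safety outputs do not restore the split:
- SAP 1.9.1 tabulates adverse events by treatment group plus an overall column, and SAP 1.9.2 gives laboratory data by the Section 1.9 groups.
- SAP Table 1-2 breaks adverse events down by region and weight, and serious and drug-related events by region only. Week 24 response is not a subgroup variable in Table 1-1.
- For the Follow-Up Period, "Group 3 and Group 4 defined in Section 1.2 will be used next to a combined group", but those tables do not cover Treatment Period 2 events.
- The Entire Treatment Period is analysed without treatment groups.
- SAP 1.10 does not name its columns for adverse events of special interest; that they follow Section 1.9 is an inference.
- The listings in SAP 1.1 and 1.10 are not summaries by group.

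**The concern.** The 2-weekly column contains no Week 24 PASI 90 responders, while most of the 4-weekly column consists of them. A difference in event rates between these columns could come from the dosing interval, from whatever separates full from partial responders, or from both. The tables alone do not let a reader tell which. The trial already randomises for the unconfounded contrasts, Group 4 with Group 3 and Group 2 with Group 1, but the safety plan does not display them.

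This bears on a stated purpose. Protocol 3.2 gives a comparable safety profile as part of the rationale for both experimental regimens, Protocol 2.3 lists safety of the different maintenance regimens as an objective, and Protocol 3.3 notes that the 2-weekly regimen had not been tested in maintenance. The 2-weekly comparison is also the one most exposed to the mixing, which could create an apparent difference or hide a real one.

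**Working it through.** **Inputs from the documents.** Planned sizes are 570 per group for Groups 1 and 2 (Protocol 9.7, SAP 1.11) and 105 per group for Groups 3 and 4 (Protocol 9.7.1). The latter reproduces: 13.3% of 1580 = 210.1, hence 210, or 105 per group.

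**Make-up of the 4-weekly column.** 570 + 105 = 675. Group 1 share = 570/675 = 84.4%; Group 3 share = 105/675 = 15.6%.

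**Shift caused by pooling alone.** Let *a* be the event rate in PASI 90 responders and *b* the rate in partial responders, with no dosing effect. The pooled 4-weekly rate is (570*a* + 105*b*)/675. Then:
- 2-weekly minus 4-weekly = 0.844 × (*b* − *a*)
- 6-weekly minus 4-weekly = −0.156 × (*b* − *a*)

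Both shifts are zero for Group 4 minus Group 3 and for Group 2 minus Group 1.

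**Assumed rates.** The documents give no event rate by Week 24 response, so *a* and *b* below are assumptions. The root-mean-square error (RMSE) is for the 2-weekly minus 4-weekly difference:
- pooled: √( *b*(1−*b*)/105 + [570*a*(1−*a*) + 105*b*(1−*b*)]/675² + shift² )
- within stratum (Group 4 minus Group 3): √( 2*b*(1−*b*)/105 )

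For *a* = 50% and *b* = 55%, the pooled terms are 0.002357 + 0.000370 + 0.001783 = 0.004510, whose root is 6.7 points. The within-stratum term is 0.004714, whose root is 6.9 points.

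| *a* | *b* | Shift, 2-weekly − 4-weekly | Shift, 6-weekly − 4-weekly | RMSE pooled | RMSE within stratum |
|---|---|---|---|---|---|
| 50% | 55% | +4.2 | −0.8 | 6.7 | 6.9 |
| 50% | 45% | −4.2 | +0.8 | 6.7 | 6.9 |
| 50% | 50% | 0 | 0 | 5.2 | 6.9 |
| 10% | 12% | +1.7 | −0.3 | 3.8 | 4.5 |
| 10% | 8% | −1.7 | +0.3 | 3.3 | 3.7 |
| 10% | 10% | 0 | 0 | 3.1 | 4.1 |

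(Shifts and errors in percentage points.)

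**Break-even.** Setting the two RMSE formulas equal, the within-stratum contrast has the smaller error once the strata differ by about 5.3 points in either direction at *a* = 50%, or by about 3.7 points upward or 2.7 points downward at *a* = 10%.

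**Precision.** The 95% half-width is 1.96 × √( *p*(1−*p*)(1/*n* + 1/*m*) ):
- 2-weekly against 4-weekly: at *p* = 50%, 10.3 points pooled (105 and 675) and 13.5 within stratum (105 and 105); at *p* = 10%, 6.2 and 8.1.
- 6-weekly against 4-weekly: at *p* = 50%, 5.6 pooled (570 and 675) and 5.8 within stratum (570 and 570); at *p* = 10%, 3.3 and 3.5.

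**The case against.** The pooling is a deliberate choice, stated openly and consistently in protocol and SAP. Tabulating by regimen received answers the objective of describing the different maintenance regimens. SAP 2.2.4 specifies only a one-sample "95% confidence interval for the relative frequency based on the score method including continuity correction" for each column, with no between-column safety test or model, so the confounded contrast is not itself a specified analysis. Nothing in the documents shows that Week 24 response predicts adverse events. Protocol 3.3 expects no safety concern with the 2-weekly regimen, and Protocol 3.2 cites an earlier study in which "psoriasis patients have been exposed to an increased drug exposure without detection of any safety-related signals". In every case tabulated above, the pooled contrast has the smaller RMSE. The 6-weekly shift, 0.3 to 0.8 points where the strata differ, is trivial beside half-widths of 3.3 to 5.8.

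Nearly all of this stands. It rules out calling the pooling an error or replacing it. It does not remove the gap: the protocol says the columns will be compared, readers will compare them, and only a split of the 4-weekly column shows whether the response strata differ.

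A reader might go further and infer that the safety conclusions are biased, or that the within-stratum contrast is the more accurate one. The documents support neither. The distortion cannot be sized from them, and the precision lost by using Group 3 alone can outweigh the bias removed.

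**Conclusion.** The point holds as an interpretability gap in descriptive tables. It is not a contradiction between the documents, and it touches no confirmatory conclusion. At planned sizes, 84.4% of any event-rate difference between the Week 24 response strata would appear as a 2-weekly against 4-weekly difference. The corresponding 15.6% for 6-weekly against 4-weekly, in the opposite direction, is negligible. The mixing weights rest on the planned 570 and 105 per group and will move with actual enrolment. Every shift in percentage points rests on assumed event rates, and the true shift may be zero. What is missing is one split, Group 1 from Group 3, since the other two dosing columns are already single randomised groups. The case is for showing both layouts, because neither dominates: pooling is more precise, and the split removes the confounding with response.

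**What to change.** In SAP 1.9, keep the pooled columns and also show Group 1 and Group 3 separately in the Treatment Period 2 tables of adverse events, serious adverse events, adverse events of special interest and key laboratory data. Group 4 can then be read against Group 3, and Group 2 against Group 1. State in SAP 1.10 which columns are used. Keep the SAF-TP2 rule of analysing by treatment received, with a note that the contrast is then only approximately randomised. Wherever the report attributes a safety difference to the dosing interval, cite the within-stratum comparison beside the pooled one.

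The cost is two extra columns in descriptive tables, with no new data and no protocol amendment. SAP 1.6 already summarises exposure by group, and SAP 2.2.1 already gives a risk-difference method if one is wanted. The downside is the wider interval for Group 4 against Group 3, so uncommon events there will remain imprecise. The pooled tables lose nothing.

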#### Treatment groups for evaluation of Follow-Up Period

For the analysis of the post treatment Follow-Up Period Group 3 and Group 4 defined in Section 1.2 will be used next to a combined group.

#### Treatment groups for evaluation of Entire Treatment Period

For the evaluation of the Entire Treatment Period all patients in the SAF-TP1 will be analyzed without consideration of any treatment groups.

#### 1.9.1 Adverse events

For adverse events and other binary safety variables crude incidence rates and associated 95%-CIs will be derived.

The crude incidence of treatment emergent adverse events will be summarized by primary System Organ Class (SOC) and Preferred Term (PT). Only primary paths within MedDRA will be considered for AE reporting.

Treatment emergent adverse events are AEs which started after the first dose of study medication or events present prior to the first dose of study medication but increased in severity based on preferred term during the Treatment Period 1, Treatment Period 2 or Follow-Up Period.

The assignment of an AE to a specific treatment period is according to its start date: an AE with start date in Treatment Period 1 and ongoing in Treatment Period 2 will count for Treatment Period 1. Only in case of increased severity in Treatment Period 2 it will also count for Treatment Period 2.

AEs will be summarized by presenting, for each treatment group (including "any AIN457"), the number and percentage of subjects having at least one AE, having an AE in each primary SOC and having each individual AE (preferred term). Summaries will also be presented for AEs by severity and for study treatment related AEs, i.e. AEs for which a possible causal relationship to the study drug has been stated in the eCRF. If a particular AE 'severity' is missing, this variable will be listed as missing and treated as missing in summaries.

If a subject reported more than one adverse event with the same preferred term, the adverse event with the greatest severity will be presented. If a subject reported more than one adverse event within the same primary system organ class, the subject will be counted only once with the greatest severity at the system organ class level, where applicable. The same algorithm applies to study treatment related AEs.

The MedDRA version used for reporting the adverse events will be described in a footnote.

Separate summaries will be provided for deaths, serious adverse events and adverse events leading to study drug discontinuation.

The adverse events will be summarized as crude incidence rates by subgroup as indicated in Table 1-1.

Non-treatment emergent adverse events will be summarized as well. These adverse events occurring before the first dose of the study treatment will be listed.

Separate summaries will be provided for liver-related adverse events and liver-related adverse events where causal relationship to study treatment at least cannot be excluded. Liver events are defined in the protocol and reported in the eCRF.

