7.1 Adverse events

An AE is any untoward medical occurrence (ie, any unfavorable and unintended sign [including abnormal laboratory findings], symptom or disease) in a patient or clinical investigation patient after providing written informed consent for participation in the study. Therefore, an AE may or may not be temporally or causally associated with the use of a medicinal (investigational) product. Study drug includes the investigational drug under evaluation and the comparator treatment that is given during any phase of the study. Medical conditions/diseases present before starting study drug are only considered AEs if they worsen after starting study drug.

All patients who have signed informed consent and are entered into the next period of the study will have all AEs occurring after informed consent is signed recorded on the AE eCRF.

The occurrence of AEs should be sought by non-directive questioning of the patient at each visit during the study. Adverse events also may be detected when they are volunteered by the patient during or between visits or through physical examination, laboratory test, or other assessments.

Abnormal laboratory values or test results constitute AEs only if they fulfill at least one of the following criteria:

- they induce clinical signs or symptoms.
- they are considered clinically significant.
- they require therapy.

Clinically significant abnormal laboratory values or test results should be identified through a review of values outside of normal ranges/clinically notable ranges, significant changes from Baseline or the previous visit, or values which are considered to be non-typical in patient with underlying disease. Investigators have the responsibility for managing the safety of individual patient and identifying AEs. Alert ranges for labs and other test abnormalities are included in Appendix 1.

Adverse events should be recorded in the AE eCRF with the following information:

- Severity grade:
 - o Mild: usually transient in nature and generally not interfering with normal activities.
 - o Moderate: sufficiently discomforting to interfere with normal activities.
 - Severe: prevents normal activities.
- Relationship of the AE to the study drug(s) (Suspected: Yes or No)
- Duration (start and end dates, or if the event is ongoing at the final examination).
- Whether it constitutes a SAE (see Section 7.2.1).
- Action taken with the study treatment.
- Concomitant medication or therapies taken.
- Outcome

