# 1.5 Subject disposition, background and demographic characteristics

#### 1.5.1 Subject disposition

The total number of subjects screened and of subjects in the SAF-TP1 set will be presented. In addition, the reasons for screen failures will be provided.

The number and percentage of subjects in the SAF-TP1 who completed Treatment Period 1 and who discontinued the study prematurely (including the reason for discontinuation) in this period will be presented.

The number of patients in the SAF-TP2 and the numbers of patients in the FAS-P90R set and in the FAS-P75R set will be provided. The numbers and percentages of subjects in the FAS-P90R and in the FAS-P75R who completed Treatment Period 2 and who discontinued the study prematurely (including the reason for discontinuation) in this period will be presented. Furthermore, the numbers of patients in the PP-P90R, PP-FUS and in the FUS will be presented.

Reportable protocol deviations as defined in the final protocol deviation (PD) Edit Check Specification will be presented in terms of absolute numbers and percentages separately for each study period (Treatment Period 1, Treatment Period 2, Follow-Up Period) for the SAF-TP1, the FAS-P90R and the FAS-P75R.

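### A run-in adverse event that becomes serious or leads to stopping study drug after Week 24, with no rise in severity grade, is missing from the adverse event tables by dosing interval

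*SAP*

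**What the plan says.** SAP 1.9 analyses safety separately for Treatment Period 1, Treatment Period 2 and follow-up. Only the Treatment Period 2 tables compare the three dosing intervals: 2-weekly (Group 4), pooled 4-weekly (Groups 1 and 3) and 6-weekly (Group 2).

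SAP 1.9.1 sets the period rule: "The assignment of an AE to a specific treatment period is according to its start date". It spells out the consequence: "an AE with start date in Treatment Period 1 and ongoing in Treatment Period 2 will count for Treatment Period 1". One exception follows: "Only in case of increased severity in Treatment Period 2 it will also count for Treatment Period 2".

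The same section adds: "Separate summaries will be provided for deaths, serious adverse events and adverse events leading to study drug discontinuation". It gives these summaries no period rule of their own, and neither does Protocol 9.5.2.

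For the entire treatment period, "all patients in the SAF-TP1 will be analyzed without consideration of any treatment groups".

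Protocol 7.1 grades severity as mild, moderate or severe, the top grade being "Severe: prevents normal activities". Whether an event is serious is a separate item in the same list. Protocol 7.2.1 defines seriousness by criteria such as hospitalisation or medical significance, not by grade.

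**The concern.** The exception depends on severity grade alone. The outcomes that matter most in a tolerability comparison, becoming serious and causing a patient to stop drug, can occur without any change of grade. If they occur after Week 24 in an event that began in the run-in, they happen under the randomised interval but are credited to the common run-in regimen.

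Safety and tolerability of the maintenance regimens is a stated objective (Protocol 2.3). Protocol 3.3 says that the 2-weekly regimen had not been tested in a maintenance period, and Protocol 8.4 provides no data monitoring committee. The Treatment Period 2 tables are the planned comparison of adverse events by regimen, so a rule that leaves such outcomes out of them deserves attention even if few patients are involved.

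**Working it through.** There is no figure in the plan to reproduce. The check applies the written rule to cases and then looks for another table that would show them.

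**Step 1. Apply SAP 1.9.1 to an event that starts in the run-in and continues past Week 24.**

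| What happens in Treatment Period 2 | Grade rises? | Counts in Period 1 | Counts in Period 2, by interval |
|---|---|---|---|
| Mild event becomes moderate | Yes | Yes | Yes |
| Moderate event leads to hospitalisation, grade unchanged | No | Yes | No |
| Moderate event leads to stopping drug at Week 32, grade unchanged | No | Yes | No |
| Event already severe becomes serious or leads to stopping drug | Not possible | Yes | No |
| Event proves fatal | Depends on the case | Yes | Through a grade rise only; no separate rule for the death summary |

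In the third row, read literally, the patient is counted as having an event leading to discontinuation in Treatment Period 1, a period that the patient completed.

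**Step 2. Can this arise under the protocol's own procedures?** Yes. In Protocol Table 14-2, for ALT or AST above 5 and up to 8 times the upper limit of normal, the trigger for a drug stop is persistence beyond two weeks, not a higher grade. Safety samples are drawn at Week 24, and SAP 1.2 runs Treatment Period 1 to the Week 24 pre-dose point. An elevation first found in that sample, or at an unscheduled visit shortly before it, has a run-in start date, while a stop for persistence falls in Treatment Period 2.

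**Step 3. Does another planned adverse event table show the case by interval?** The entire-period tables have no treatment groups. The follow-up tables cover only the period after Week 52 in Groups 3 and 4. No other adverse event table is split by interval.

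**Step 4. Scale of one missed patient.** Inputs are the planned group sizes: 570 each in Groups 1 and 2 (Protocol 9.7) and 105 each in Groups 3 and 4 (Protocol 9.7.1). The change in incidence is 1/n.

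- 2-weekly: 1/105 = 0.95 percentage points.
- 6-weekly: 1/570 = 0.18 percentage points.
- Pooled 4-weekly: n = 570 + 105 = 675; 1/675 = 0.15 percentage points.

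The documents do not say how many run-in events will be ongoing at Week 24, or how many of those will later become serious or lead to a drug stop at the same grade. The total effect cannot be computed.

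**The case against.** The strongest defence is that the rule is deliberate and even-handed. Filing by onset avoids charging a randomised interval with events that began under the common run-in regimen, and it treats all arms alike. The severity exception then returns many run-in events that turn serious or fatal, because these often rise in grade. SAP 1.1 also presents listings by treatment sequence, so listed cases remain traceable to the regimen.

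Much of this stands. Onset is a sound basis for the general adverse event tables, and a reader might wrongly infer that every run-in event that becomes serious, fatal or leads to a stop disappears from the tables by interval. The sentence following the quoted rule rules that out. What the defence does not cover is the unchanged-grade event. Its onset precedes randomisation, but its serious outcome or drug stop follows it and may depend on the interval. A listing does not put it into an incidence rate.

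Four other stronger readings do not hold:

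- **Conflict with disposition.** SAP 1.5.1 gives numbers and percentages of patients "who completed Treatment Period 2 and who discontinued the study prematurely (including the reason for discontinuation) in this period will be presented". A reader might infer that this must contradict the adverse event table. But it counts study discontinuation, and Protocol 5.5.10 states that stopping study drug is not the same as leaving the study. The analysis sets differ too. The tables may differ without either being wrong. Nor does disposition replace the missing count, since it is not specified by preferred term or in the pooled safety columns.
- **A proportional understatement.** A reader might suppose that some share of Treatment Period 2 stops, say 10–30%, began in the run-in, and infer that rates by regimen are too low by that share. The documents give no such share, and any assumed share would be a ceiling, because events that rise in grade are retained.
- **An unworkable exception.** Protocol 7.1 lists no date for a change of grade, which might suggest that the exception cannot be applied. But the same section asks for changes in severity to be assessed at each visit, and its list is not the eCRF specification.
- **Deaths misfiled.** The SAP does not expressly say that the death summary follows adverse event onset. The rule for deaths is unstated, which is different from being wrong.

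**Conclusion.** The point holds for one defined class of events: run-in onset, ongoing past Week 24, then becoming serious or leading to a study drug stop in Treatment Period 2 with no increase in grade. Under SAP 1.9.1 as written, these count only in Treatment Period 1 and in no adverse event table by dosing interval. This is more than a missing detail, because a stated rule assigns a post-randomisation outcome to a period that the patient had completed. For deaths, the gap is that no period rule is given.

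The number of such events is unknown and probably small. A single event matters most in the 2-weekly column, at 0.95 percentage points. These per-patient figures assume that the planned group sizes are reached. The conclusion also assumes that the serious-event and discontinuation summaries follow the only period rule that SAP 1.9.1 gives. The efficacy analyses are not affected.

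**What to change.** Extend the existing exception in SAP 1.9.1: a run-in adverse event also counts for Treatment Period 2 if, in that period, its severity increases, it becomes serious, it is fatal, or it leads to study drug discontinuation. Using the same exception keeps the tables consistent, because an event in the Treatment Period 2 serious-event table will also be in the Treatment Period 2 adverse event table.

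Then give the three separate summaries their own dates:

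- Adverse events leading to study drug discontinuation: the recorded date of stopping drug (Protocol 5.5.10 requires it).
- Deaths: the date of death.
- Serious adverse events: the date on which the event became serious, where the serious adverse event report gives it. Protocol 7.1 does not list this date, so the SAP should state what is done when it is missing.

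Start-date assignment stays for all other run-in events. The cost is a few SAP sentences, a footnote and a small programming change. The drawback is that some events with run-in onset will appear in the Treatment Period 2 columns, which the footnote should say.
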